### **6.2 PRIMARY OBJECTIVE AND STATISTICAL JUSTIFICATION FOR SAMPLE SIZE**

This study will be conducted as a prospective, randomized two arm, pilot trial to explore the utility of TARP peptide vaccination alone or vaccination with TARP peptide-pulsed dendritic cells in patients with Stage D0 prostate cancer.

The primary objective is to obtain a reliable estimate of the immunologic response rate to vaccination with either peptide vaccine or dendritic cells in patients with biochemical progression and to determine if the rate of immunologic response in either arm is adequate to warrant further investigation in subsequent studies. Evaluation of safety and toxicity will also be a primary goal. The study is not designed to have adequate power to identify if one arm is associated with a significantly improved immunologic response rate as compared to the other, as such detection may require very large numbers of patients given the potential similarity of the arms. Furthermore, there is no requirement that only one arm be selected for further development. Should both arms demonstrate adequate immunologic responses, then future studies will consider either or both arms depending on immune responses, feasibility, toxicity and other outcomes such as PSADT.

Patients will initially be screened for HLA-A\*0201 positivity. HLA-A\*0201 patients will then undergo comprehensive protocol eligibility screening and if found to be eligible, will be enrolled in the study. Upon enrollment patients will be randomized in a 1:1 manner to receive TARP peptide vaccination with Montanide® ISA51 VG plus GM-CSF (Arm A) or TARP peptide-pulsed dendritic cells (Arm B).

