For each arm, using an acceptable immunologic response rate of 40% ( $p_1=0.40$ ) and an unacceptable rate of 10% ( $P_0=0.10$ ) and using a two-stage optimal design (Simon R, *Controlled Clinical Trials* 10:1-10, 1989) with  $\alpha = 0.05$  and  $\beta = 0.10$ , we will initially accrue 9 patients in each arm. An unacceptable response rate of 10% (or less) and an acceptable response rate of 40% were determined based on historical clinical trial response rates to vaccines and immune-based therapies for cancer. If 0-1 patients develop an immunologic response as defined in Section 5.2.1, then no further patients will be enrolled. If 2 or more of these 9 patients develop an immunologic response, we will accrue 11 additional patients for a maximum total of 20 patients per arm. If 2-4 of 20 has an immunologic response, then the results from this arm will be considered inadequate for further investigation. If 5 or more of these 20 has an immune response, we will be able to conclude that the vaccine on the given arm is worthy of further development in this population on the basis of immune response. Under the null hypothesis ( $p_0=0.20$ ), the probability of early termination is 77%.

There is no requirement that only one arm be selected for further development; should both arms demonstrate adequate immunologic responses, then future studies will consider either or both arms depending on immune responses, feasibility, toxicity and other outcomes such as PSADT.

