As stated in Section 3.3.2, an early stopping rule will be used to ensure that the study subjects do not have exposure to excessive toxicity: If more than one of the first nine subjects on a given arm experiences dose limiting toxicity (defined in Section 3.3.1), enrollment will cease for that arm and revisions to the treatment will be discussed with the IRB and FDA. This is because 1/9 has an upper one-sided 90% confidence interval limit of 37%, while 2/9 has an upper one-sided 90% confidence interval limit of 49%; the former would be marginally acceptable as a rate of toxicity while the latter is not. In addition, any unusually severe toxicity noted may result in temporary suspension of accrual pending re-evaluation of the agent. All toxicities noted will be tabulated by type and grade, for each arm. Any such toxicities that appear in at least 5 patients on either arm will also have the distribution of grades of that toxicity compared between the arms using an exact Cochran-Armitage test.

The percent of patients who meet PSADT response criteria as outlined in section 5.2.2 will also be evaluated as a secondary endpoint. In addition, exploratory comparisons of PSADT among study time points will be performed as outlined in Sections 3.1 and 5.2.2. Given that there will be 6 separate comparisons of PSADT, we will only report differences with  $p < 0.01$  as being statistically significant while other differences with  $0.01 < p < 0.05$  will be considered to be trends. Appropriate 95% confidence intervals will be constructed and reported which takes into consideration the two-arm nature of the design. No formal comparison will be undertaken since the study does not have adequate power to address this comparison properly.

It is expected that 1-2 patients per month may be enrolled onto this study. Based on accrual of 18-20 patients per year, accrual should be completed in approximately 2 to 2.5 years if all 40 patients were to be required. To allow for the possibility of inevaluable patients, an accrual ceiling of 43 will be used.

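### Does a 95% interval that can still contain 10% at 5 of 20 responders undercut the rule that passes an arm at 5 of 20?

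*Combined protocol and SAP*

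**What the plan says.** Section 6.2 gives each arm a Simon optimal two-stage design with alpha 0.05 and beta 0.10. On the benchmark rates it says "An unacceptable response rate of 10% (or less) and an acceptable response rate of 40% were determined". Nine patients enter first, and the arm stops at 0 or 1 responder. Otherwise 11 more enter. A final total of 2 to 4 of 20 is inadequate. At 5 or more the plan says "we will be able to conclude that the vaccine on the given arm is worthy of further development in this population".

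Estimation is also part of the aim: "The primary objective is to obtain a reliable estimate of the immunologic response rate to vaccination". The interval statement comes later in Section 6.2, directly after the text on PSADT response and the PSADT comparisons: "Appropriate 95% confidence intervals will be constructed and reported which takes into consideration the two-arm nature of the design". It does not say which endpoint is meant, which method is used, or whether the limits are one- or two-sided. In the same section the toxicity rule is justified by one-sided limits: "1/9 has an upper one-sided 90% confidence interval limit of 37" per cent, with 49% for 2/9.

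**The concern.** The pass rule and the interval appear to answer the same question at different levels. The rule is one-sided at 5%, while a central two-sided 95% interval leaves 2.5% in each tail. A result whose one-sided p-value lies between 0.025 and 0.05 passes the rule, yet its interval still reaches the unacceptable rate. The lowest passing result, 5/20, is such a result.

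A reader who judged an arm by whether a central exact interval excluded 10% would in effect require 6/20, and at that bar power at a true 40% is below the planned 90%. Because no method is named, whether the interval excludes 10% could also depend on a choice made after the data are seen.

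**Working it through.** **Inputs (Section 6.2).** p0 = 0.10, p1 = 0.40; stop at 0–1 of 9; 11 more patients; pass at 5 or more of 20.

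**Reproducing the plan's figures.** Early termination at 10% is P(X ≤ 1 of 9) = 0.9^9 + 9 × 0.1 × 0.9^8 = 0.387 + 0.387 = 0.775, which matches the stated 77%. (The plan prints p0 = 0.20 beside that figure. At 20% the probability is 0.8^9 + 9 × 0.2 × 0.8^8 = 0.134 + 0.302 = 0.436, so the label is a slip that does not bear on this point.)

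The probability of reaching at least s responders of 20 is

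P(s; p) = Σ over x = 2…9 of Bin(x; 9, p) × P(Y ≥ s − x), with Y ~ Bin(11, p).

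- P(5; 0.10) = 0.0349 and P(5; 0.40) = 0.902. The design meets alpha 0.05 and power 90%. A search over two-stage designs returns the same one as optimal.
- P(4; 0.10) = 0.0911 and P(6; 0.10) = 0.0101.

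The two-stage p-value at 5/20 is therefore 0.0349, below 0.05 and above 0.025. That gap is the whole of the mismatch.

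**95% limits at 5/20, by method.**

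| Method | Lower | Upper | Contains 10%? |
|---|---|---|---|
| Wald: 0.25 ± 1.96 × √(0.25 × 0.75/20) | 6.0% | 44.0% | yes |
| Clopper-Pearson | 8.7% | 49.1% | yes |
| Two-stage exact, central | 9.2% | 51.8% | yes |
| Mid-P | 9.8% | not computed | yes |
| Jeffreys | 10.2% | 46.4% | no |
| Blaker or Sterne (non-central exact) | about 10.4% | about 47.4% | no |
| Agresti-Coull | 10.8% | 47.2% | no |
| Wilson | 11.2% | 46.9% | no |

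Blaker and Sterne are also exact methods. At p = 0.10 with fixed n = 20, the upper tail P(X ≥ 5) is 0.043. The smallest possible lower tail is P(X = 0) = 0.9^20 = 0.122, which is larger, so nothing is added from that side. The two-sided exact p-value stays at 0.043, and 10% is excluded.

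**Neighbouring totals.** At 6/20 the lower limits are 11.9% (Clopper-Pearson) and 12.2% (two-stage exact), so 10% is excluded. At 4/20 they are 5.7% and 6.5%, and the arm fails. With the central exact methods the disagreement is confined to 5/20.

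**How often an arm ends at exactly 5/20: P(5; p) − P(6; p).**

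| True rate | Pass at 5+ | Pass at 6+ | Exactly 5/20 |
|---|---|---|---|
| 10% | 3.5% | 1.0% | 2.5% |
| 20% | 31.5% | 17.9% | 13.6% |
| 30% | 68.7% | 54.8% | 13.9% |
| 40% | 90.2% | 84.4% | 5.8% |

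**What the plan does with the interval.** The count rule in Section 6.2 covers every outcome: 0–1 of 9, 2–4 of 20, and 5 or more of 20. No section gives an interval a role in judging response. The 84.4% power belongs to a 6/20 bar that the plan does not contain.

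**The case for a change.** The best case for a change has three parts.

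First, exact methods look like the plan's habit. Its toxicity limits reproduce as exact one-sided limits (36.8% and 49.0%), and it specifies an exact Cochran-Armitage test. A central exact interval is therefore a likely choice for the response rate, and it contains 10% at 5/20. This is fair as a forecast. But the plan does not commit to that interval, so a conflict with the interval it promises is not shown. The toxicity comparison goes no further: those limits are the stated reason for the toxicity rule, whereas the response rule rests on its own error rates.

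Second, 5/20 is not remote. For two arms with the same true rate, the chance that at least one ends there is 1 − (1 − 0.136)² = 25% at 20%, and 26% at 30%. It also makes up 71% of passes at a true 10%. Those figures stand, though the 71% is 2.5 of only 3.5 percentage points. Neither figure alters a decision, because the count decides.

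Third, the sentence sits among the PSADT text. If it covers PSADT only, the primary estimate has no stated interval. That is the part with most substance. Still, given the estimation aim, an analyst would report a 95% interval for each arm's response rate in any case, and any recognised method is defensible if named in the report.

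**Conclusion.** The arithmetic is right, but it describes a difference of convention and not a fault. A one-sided 5% test and a central two-sided 95% interval will disagree for some results near the boundary. Here that means one total of 21, with probability 2.5% to 13.9% per arm at true rates of 10%, 20%, 30% and 40%. An interval reported for estimation need not invert the decision test.

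Followed as written, the plan gives a sound go/no-go decision (type I error 3.5%, power 90.2%) and leaves room for a valid interval. What is missing is the endpoint and method for one reporting sentence, and analysts can supply both without harm. Adding a 90% interval would line up with the rule, with lower limits of 10.4% (Clopper-Pearson) or 11.0% (two-stage exact) at 5/20. That is a reporting preference and changes no result.

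This rests on two assumptions. One is that the interval sentence covers the immunologic response rate, which is an inference from its place in Section 6.2. The other is that each arm has exactly 9 and then 11 evaluable patients and stops early only for lack of immune response. The toxicity stop and the allowance in "To allow for the possibility of inevaluable patients, an accrual ceiling of 43 will be used" could shift the two-stage figures, but they do not change the reasoning.

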## **7 SAFETY REPORTING REQUIREMENTS/DATA AND SAFETY MONITORING PLAN**

At each study visit, patients will be evaluated for new or evolving AEs. Symptoms will be elicited through the use of open-ended questions, followed by appropriate questions that clarify the patient's verbatim description of AEs or changes in concomitant medications. A review of systems will be performed.

The Principal Investigator or Lead Associate Investigator will assess whether the AE or SAE is associated with the administration of TARP peptide vaccine:

- Unrelated, Unlikely, Possible, Probably, Definite

### **7.1 DEFINITIONS**

#### **7.1.1 Adverse Event**

Any untoward medical occurrence in a human subject, including any abnormal sign (for example, abnormal physical exam or laboratory finding), symptom, or disease, temporally associated with the subject's participation in research, whether or not considered related to the subject's participation in the research

- If any abnormal laboratory result is considered clinically significant, the investigator will provide details about the action taken with respect to the test drug and about the patient's outcome.

#### **7.1.2 Suspected adverse reaction**

Suspected adverse reaction means any adverse event for which there is a reasonable possibility that the drug caused the adverse event. For the purposes of IND safety reporting, 'reasonable possibility' means there is evidence to suggest a causal relationship between the drug and the adverse event. A suspected adverse reaction implies a lesser degree of certainty about causality than adverse reaction, which means any adverse event caused by a drug.

#### **7.1.3 Unexpected adverse reaction**

An adverse event or suspected adverse reaction is considered "unexpected" if it is not listed in the investigator brochure or is not listed at the specificity or severity that has been observed; or, if an investigator brochure is not required or available, is not consistent with the risk information described in the general investigational plan or elsewhere in the current application.

"Unexpected", also refers to adverse events or suspected adverse reactions that are mentioned in the investigator brochure as occurring with a class of drugs or as anticipated from the pharmacological properties of the drug, but are not specifically mentioned as occurring with the particular drug under investigation.

#### **7.1.4 Serious**

An Unanticipated Problem or Protocol Deviation is serious if it meets the definition of a Serious Adverse Event or if it compromises the safety, welfare or rights of subjects or others.

#### 7.1.5 Serious Adverse Event

An adverse event or suspected adverse reaction is considered serious if in the view of the investigator or the sponsor, it results in any of the following:

- Death,
- A life-threatening adverse drug experience
- Inpatient hospitalization or prolongation of existing hospitalization
- Persistent or significant incapacity or substantial disruption of the ability to conduct normal life functions
- A congenital anomaly/birth defect.
- Important medical events that may not result in death, be life-threatening, or require hospitalization may be considered a serious adverse drug experience when, based upon appropriate medical judgment, they may jeopardize the patient or subject and may require medical or surgical intervention to prevent one of the outcomes listed in this definition.

#### 7.1.6 Disability

A substantial disruption of a person's ability to conduct normal life functions.

#### 7.1.7 Life-threatening adverse drug experience

Any adverse event or suspected adverse reaction that places the patient or subject, in the view of the investigator or sponsor, at immediate risk of death from the reaction as it occurred, i.e., it does not include a reaction that had it occurred in a more severe form, might have caused death.

#### 7.1.8 Protocol Deviation (NIH Definition)

Any change, divergence, or departure from the IRB-approved research protocol.

#### 7.1.9 Non-Compliance (NIH Definition)

The failure to comply with applicable NIH Human Research Protections Program (HRPP) policies, IRB requirements, or regulatory requirements for the protection of human research subjects.

#### 7.1.10 Unanticipated Problem

Any incident, experience, or outcome that:

- Is unexpected in terms of nature, severity, or frequency in relation to
  - (a) the research risks that are described in the IRB-approved research protocol and informed consent document; Investigator's Brochure or other study documents, and
  - (b) the characteristics of the subject population being studied; **AND**
- Is related or possibly related to participation in the research; **AND**
- Suggests that the research places subjects or others at a *greater risk of harm* (including physical, psychological, economic, or social harm) than was previously known or recognized.

## **7.2 NIH INTRAMURAL IRB AND CLINICAL DIRECTOR REPORTING**

### **7.2.1 NIH Intramural IRB and NCI CD Expedited Reporting of Unanticipated Problems and Deaths**

The Protocol PI will report in the NIH Problem Form to the NIH Intramural IRB and NCI Clinical Director:

- All deaths, except deaths due to progressive disease
- All Protocol Deviations
- All Unanticipated Problems
- All non-compliance

Reports must be received within 7 days of PI awareness via iRIS.

### **7.2.2 NIH Intramural IRB Requirements for PI Reporting at Continuing Review**

The protocol PI will report to the NIH Intramural IRB:

1. A summary of all protocol deviations in a tabular format to include the date the deviation occurred, a brief description of the deviation and any corrective action.
2. A summary of any instances of non-compliance
3. A tabular summary of the following adverse events:
  - All Grade 2 **unexpected** events that are possibly, probably or definitely related to the research;
  - All Grade 3 and 4 events that are possibly, probably or definitely related to the research;
  - All Grade 5 events regardless of attribution;
  - All Serious Events regardless of attribution.

**NOTE:** Grade 1 events are not required to be reported.

### **7.2.3 NIH intramural IRB Reporting of IND Safety Reports**

Only IND Safety Reports that meet the definition of an unanticipated problem will need to be reported to the NIH Intramural IRB.

## **7.3 IND SPONSOR REPORTING CRITERIA**

An investigator must **immediately** report to the sponsor, using the mandatory MedWatch form 3500a, any serious adverse event, whether or not considered drug related, including those listed in the protocol or investigator brochure and must include an assessment of whether there is a reasonable possibility that the drug caused the event.

- All Grade 5 (fatal) events (except death due to progressive disease) must be reported via email within 24 hours. A complete report must be submitted within one business day.
- All other serious adverse events including deaths due to progressive disease must be reported within one business day

Study endpoints that are serious adverse events (e.g. all-cause mortality) must be reported in accordance with the protocol unless there is evidence suggesting a causal relationship between the drug and the event (e.g. death from anaphylaxis). In that case, the investigator must immediately report the death to the sponsor.

Events will be submitted to Center for Cancer Research (CCR) at: [[contact]](mailto:[contact]) and to the CCR PI and study coordinator.

## **7.4 DATA AND SAFETY MONITORING PLAN**

### **7.4.1 Principal Investigator/Research Team**

The Principal Investigator and Lead Associate Investigator will monitor this pilot, prospective randomized study, as required by the FDA as part of the Sponsor Investigator IND held by the Principal Investigator. Based on the minimal risk and the limited number of subjects to be studied, monitoring by a Data Safety Monitoring Board is not warranted for this trial. There will be continuous close monitoring of protocol-related toxicity by the Lead Associate Investigator and Principal Investigator. The study research nurse coordinator and/or data manager will generate a bi-weekly (or weekly) reports of all on-study laboratory data with correspondent toxicity grading according to CTCAE v3.0 as well as a summary of all clinical and Vaccine Report Card (VRC) surveillance adverse event data for review by the Principal Investigator and The Lead Associate Investigator in conjunction with Associate Investigators. In addition, study summaries will be generated every 6 months and forwarded to the FDA. Adverse events will be reported to the IRB as described in section 7.2. Decisions regarding revision of the protocol or consent will be promptly communicated to the IRB and FDA.

### **7.4.2 Sponsor Monitoring Plan**

As a sponsor for clinical trials, FDA regulations require the CCR to maintain a monitoring program. The CCR's program allows for confirmation of: study data, specifically data that could affect the interpretation of primary study endpoints; adherence to the protocol, regulations, and SOPs; and human subjects protection. This is done through independent verification of study data with source documentation focusing on:

- Informed consent process
- Eligibility confirmation
- Drug administration and accountability
- Adverse events monitoring
- Response assessment.

The monitoring program also extends to multi-site research when the CCR is the coordinating center.

This trial will be monitored by personnel employed by an NCI contractor. Monitors are qualified by training and experience to monitor the progress of clinical trials. Personnel monitoring this study will not be affiliated in any way with the trial conduct.

## **8 HUMAN SUBJECTS PROTECTION**

### **8.1 RATIONALE FOR SUBJECT SELECTION**

All subjects enrolled in this study will be male as the disease under study does not affect women or children. We will make every effort to accrue patients from all racial and ethnic groups. Since our referral population is the nation, we should obtain referrals representative of the national composition of races. In addition, HLA-A\*0201 positivity is not restricted to a particular racial or ethnic group: it is present in 49.54% of Caucasians, 33.74% of African-Americans, and 55.87% of Orientals. Hence the requirement for HLA-A\*0201 positivity should not preclude our ability to accrue a racially and ethnically diverse population representative of individuals affected by prostate cancer.

Participants will be accrued through web-based advertisements, community-based contacts and referrals of patients from other studies at the Clinical Center. This protocol will also be advertised on the NCI PDQ Clinical Trials database as well as through ClinicalTrials.gov.

### **8.2 EVALUATION OF BENEFITS AND RISKS/DISCOMFORTS**

The benefit of vaccination with peptides is unknown. Although several patients in our previous Phase I peptide vaccine studies mounted immune responses to various peptides, the benefit or clinical significance of these immune responses remains unknown. However, in animal models, immune responses have been correlated with both a decrease in measurable disease and a subsequent resistance to tumor challenge (Ref). In this study, we will determine the impact of vaccination on PSADT, a well established surrogate marker that is a predictive factor of longer time to metastases, prostate-cancer death and all-cause adverse clinical outcomes. The risks of vaccination are also unknown. However, no severe or systemic toxicity in response to vaccination with peptides alone has been observed and the most frequent adverse event is local injection site reactions, an observation common to all vaccines.

